### 7.2.2 *Unexpected Adverse Events*

An adverse event can be considered unexpected when the nature, intensity or frequency of which is not consistent with the current adverse event list of the Investigator's Brochure, contact the lead site, principal investigator or sponsor to confirm unexpected adverse events when necessary.

## 7.3 Recording and Grading

### 7.3.1 *Recording*

All observed or volunteered adverse events, regardless of treatment group, severity, suspected causal relationship, expectedness, or seriousness will be documented.

A clinically significant change in a physical examination finding or an abnormal test result (i.e., laboratory, x-ray, EKG) should be recorded as an AE, if it:

- is associated with accompanying symptoms
- is suggestive of organ toxicity
- requires additional diagnostic testing or medical or surgical intervention
- leads to a change in study dosing or discontinuation from the study
- is considered clinically significant by the investigator.

An abnormal test result that is subsequently determined to be in error does not require recording as an adverse event, even if it originally met one or more of the above criteria.

### 7.3.2 *Grading severity*

All adverse events will be graded for intensity on a scale of 0 to 5. Severity grades will be recorded and based on the most recent version of the NCI CTCAE v.5.0 handbook.

### 7.3.3 *Attributing causality*

Medical judgment should be used to determine the cause of the AE considering all relevant factors such as, but not limited to, the underlying study indication, coexisting disease, concomitant medication, relevant history, pattern of the AE, temporal relationship to the study medication, dechallenge or rechallenge with the study drug (Table 4).

Table 4 *Relationship of Adverse Event to Study Drug*

Not Related To Study Drug	

• An AE that is clearly due to extraneous causes (eg, concurrent disease, concomitant medications, disease under study, etc.)

• It does not follow a reasonable temporal sequence from administration of the study drug.

• It does not follow a known pattern of response to study drug

• It does not reappear or worsen when study drug is restarted.

• An alternative explanation is likely, but not clearly identifiable.

---------------------------	--

Related to Study Drug	

• An AE that is difficult to assign to alternative causes.

• It follows a strong or reasonable temporal sequence from administration of study drug.

• It could not be reasonably explained by the patient's clinical state, concurrent disease, or other concomitant therapy administered to the patient.

• It follows a known response pattern to study drug

• It is confirmed with a positive rechallenge or supporting laboratory data.

-----------------------	--

## 7.4 Reporting Adverse Events

### 7.4.1 Reporting serious adverse events

*All SAEs and AESIs, regardless of relationship to study drug, must be reported to the lead site within 48 business hours of knowledge of the event, during the study through 30 days after receiving the last dose of study treatment, according to the procedures below. After the 28-day specified window, only SAEs considered to be treatment-related and all AESIs, regardless of treatment relationship, should be reported. It is important that the investigator provide an assessment of relationship of the SAE or AESI to study treatment at the time of the initial report.*

*The Clovis or the Sponsor-Investigator's study-specific Serious Adverse Event (SAE)/Adverse Events of Special Interest (AESI) Report Form must be used for reporting SAEs and AESIs. The contact information for reporting of SAEs and AESIs can be found on the SAE/AESI Reporting Form and Pregnancy Report Forms.*

*The Sponsor-Investigator is responsible for submitting reports of AEs associated with the use of the drug that are both serious and unexpected to the U.S. Food and Drug Administration (FDA), according to 21 Code of Federal Regulations (CFR) 312.32 ; to the Japanese Pharmaceuticals and Medical Devices Agency (PMDA); to the European regulatory authorities according to the European Commission Clinical Trials Directive (2001/20/EC); and to other applicable regulatory authorities, according to national law and/or local regulations. All investigators participating in ongoing clinical studies with the study medication will receive copies of these reports for prompt submission to their IRB or IEC. In accordance with the European Commission Clinical Trials Directive (2001/20/EC), Clovis or its designee will notify the relevant ethics committees in concerned member states of applicable suspected unexpected serious adverse reactions (SUSARs) as individual notifications or through periodic line listings.*

*The Sponsor-Investigator will submit all safety updates and periodic reports to the regulatory authorities as required by applicable regulatory requirements.*

### 7.4.2 Reporting SAEs at multi-site/participating institutions

SAEs should be reported to the lead site.

## 8. CRITERIA FOR OUTCOME ASSESSMENT/THERAPEUTIC RESPONSE

### 8.1 Outcome Assessment

All baseline evaluations will be performed as closely as possible to the beginning of treatment (within 7 days). For subsequent evaluations, the method of assessment and techniques will be the same as those used at baseline.

**Note:** Any bone lesions, however, that are identified on the baseline CT or MRI studies and judged as providing meaningful information about nontarget disease status on the basis of their size or other features should be considered for inclusion in the follow-up assessments of nontarget lesions by the same imaging modality.

- Conventional CT, Bone Scan

CT Chest, abdomen, pelvis and Bone scans will be used to measure tumor response as a secondary endpoint per RECIST 1.1 criteria (metastatic disease only).

- Tumor markers

PSA measurements will be used to assess the primary endpoint

#### 8.1.1 Primary endpoint

The primary endpoint is defined as a PSA50 response, defined as a decline in PSA to ≥50% of baseline level, confirmed with a second measurement at least 4 weeks later.

#### 8.1.2 Secondary endpoints

8.1.2.1. *Safety:* this endpoint is defined as incidence of grade 3-5 toxicities based upon CTCAE v5.0 standard grading scales.

8.1.2.2. *PSA Progression-Free Survival (PFS):* PSA progression (PSA progression-free survival; PSA-PFS) will be defined per PCWG3 guidelines

For those subjects showing an initial decline in PSA from baseline, is defined as an increase in PSA that is ≥25% and ≥2 ng/mL above the nadir, and which is confirmed by a second value 3 or more weeks later (i.e., a confirmed rising trend).

For those subjects with no decline in PSA from baseline, is defined as an increase in PSA that is ≥25% and ≥2 ng/mL after 12 weeks.

8.1.2.3. *Radiographic Progression-free survival:* time to radiographic or clinical progression or death, whichever comes first. Based on RECIST version 1.1 and PCWG3 definitions including: Progression of soft tissue lesions according to RECIST 1.1; Progression of bone lesions detected with bone scan according to PCWG3 criteria; Radiologically-confirmed spinal cord compression or pathological fracture due to malignant progression, or other clinical event deemed to be cancer-related.

8.1.2.4 Objective response rate (metastatic disease only): defined as the proportion of patients achieving a complete/partial response in target lesions (RECIST

1.1)

## 8.2 Therapeutic Response

Response and progression will be evaluated in this study using a combination of the international criteria proposed by the Response Evaluation Criteria in Solid Tumors (RECIST) Committee(17) and the guidelines for prostate cancer endpoints developed by the Prostate Cancer Clinical Trials Working Group (PCWG3).(18)

Patients will need to be reevaluated for response every cycle according to the guidelines below.

### 8.2.1 *PSA*

Perform PSA testing at a minimum of 1-week intervals with the threshold PSA level at 2.0 ng/mL. To report PSA-based outcomes, PCWG3 recommends that the percent of change in PSA from baseline to 12 weeks (or earlier for those who discontinue therapy) and the maximum decline in PSA that occurs at any point after treatment be reported for each patient using a waterfall plot. PSA measurements obtained during the first 12 weeks should not be used as the sole criterion for clinical decision making.

### 8.2.2 *Measurable disease*

According to RECIST 1.1, measurable disease is defined as at least 1 lesion > 10mm in its longest diameter as measured with conventional techniques (i.e., CT with slice cut of 5mm, MRI). All tumor measurements will be taken using a ruler or calipers and recorded in millimeters (or decimal fractions of centimeters). To be considered pathologically enlarged and measurable, a lymph node must be  $\geq 15$  mm in short axis when assessed by CT scan (CT scan slice thickness recommended to be no greater than 5 mm).

### 8.2.3 *Nonmeasurable disease*

Following RECIST, all other lesions (or sites of disease) will be considered nonmeasurable disease. This includes small lesions (longest diameter < 10 mm using spiral CT scan) lymph nodes (shortest diameter  $\geq 10$ mm to <15mm) and any of the following:

- bone lesions
- ascites
- pleural or pericardial effusion
- lymphangitis cutis or pulmonis
- abdominal masses that are not confirmed and followed by imaging techniques
- cystic lesions
- lesions occurring within a previously irradiated area unless they are documented as new lesions since the completion of radiation therapy

**Note:** If only a single, asymptomatic bone lesion is present at baseline, and will be irradiated, the metastatic nature of this lesion must be confirmed by x-ray, CT, or MRI.

**8.2.4 Target (nodal and visceral) lesions**

Following RECIST, progression in a nodal or visceral site (i.e., liver and lung) is sufficient to document disease progression. The presence or absence of nodal and visceral disease before and after treatment should be recorded separately.

All measurable lesions (up to a maximum of 2 lesions per organ and 5 lesions in total) will be identified as target lesions to be measured and recorded at baseline. The target lesions should be representative of all involved organs. Target lesions will be selected on the basis of size (i.e., the largest area) and suitability for accurate, repeated measurements (either by imaging techniques or clinically). The sum of the longest diameter (LD) of all target lesions will be calculated and reported as the baseline sum LD. The baseline sum LD will be used as a reference by which to characterize the objective tumor response.

Because small lymph nodes are difficult to measure accurately and may not be malignant, to be considered pathologically enlarged and measurable, a lymph node must be  $\geq 15$  mm in short axis when assessed by CT scan (CT scan slice thickness recommended to be no greater than 5 mm).

**8.2.5 Bone lesions**

When the bone scan is the sole indicator of progression, disease progression in bone is defined as 2 or more new lesions seen on bone scan compared with a prior scan for used trial entry. In situations where scan findings suggest a flare reaction or where new lesion(s) may represent trauma, confirm these results with other imaging modalities (eg, MRI or fine-cut CT). If many new areas of uptake are observed, confirmation is generally not necessary.

**8.2.6 Nontarget lesions**

All other lesions (or sites of disease) will be identified as nontarget lesions and recorded at baseline. Nontarget lesions will include measurable lesions that exceed the maximum number per organ (2) or total of all involved organs (5), as well as nonmeasurable lesions. The presence or absence of these lesions will be recorded on the CRF and should be evaluated at the same assessment time points as all target lesions.

**8.2.7 New lesions**

The appearance of new malignant lesions denotes disease progression. There are no specific criteria for the identification of new radiographic lesions; however, the finding of a new lesion should be unequivocal: i.e. not attributable to differences in scanning technique, change in imaging modality or findings thought to represent something other than tumour (for example, some 'new' bone lesions may be simply healing or flare of pre-existing lesions).

## **8.3 Response Criteria for Primary and Secondary Endpoints**

**8.3.1 Measurable soft-tissue lesions**

When evaluating soft-tissue lesions, the definitions in Table 5 apply.

*Table 5 RECIST1.1 response criteria for target lesions*

Response	Evaluation of Soft-Tissue Lesions
Complete response (CR)	Disappearance of all target lesions. Any pathological lymph nodes (whether target or non-target) must have reduction in short axis to <10 mm.
Partial response (PR)	At least a 30% decrease in the sum of diameters of target lesions, taking as reference the baseline sum diameters.
Progressive disease (PD)	At least a 20% increase in the sum of diameters of target lesions, taking as reference the smallest sum on study (this includes the baseline sum if that is the smallest on study). In addition to the relative increase of 20%, the sum must also demonstrate an absolute increase of at least 5 mm. (Note: the appearance of one or more new lesions is also considered progression).
Stable disease (SD)	Neither sufficient shrinkage to qualify for PR nor sufficient increase to qualify for PD, taking as reference the smallest sum diameters while on study.

In some circumstances, it may be difficult to distinguish residual disease from normal tissue. When the evaluation of complete response depends on this determination, it is recommended that the residual lesion be investigated (eg, fine needle aspirate or biopsy) before confirming the complete response status.

Changes in nodal and visceral sites should be recorded and reported separately, and lymph nodes in the pelvis must measure at least 1.5 cm in shortest diameter to be considered target lesions. Complete elimination of disease at a particular site should be recorded separately. Any favorable change should be confirmed using a second follow-up scan.

#### 8.3.2 *PSA*

For each patient, use a waterfall plot to report the percent change in PSA from baseline to 12 weeks (or earlier for those who discontinue therapy) and the maximum decline in PSA that occurs at any point after treatment. We will also report the proportion of patients to achieve a 50% of greater decrease in PSA from baseline (i.e. PSA50 response rate)

#### 8.3.3 *Bone*

Record post-treatment changes as either “no new lesions” or “new lesions.”

In the absence of clearly worsening soft-tissue (nodal and visceral) disease or disease-related symptoms, progression at the first scheduled assessment should be confirmed on a second scan performed 6 or more weeks later. In the rare case where visible lesions disappear, this too should be confirmed.

#### 8.3.4 *Nontarget lesions*

When assessing nontarget lesions, the definitions in Table 6 will apply.

**Table 6 RECIST1.1 response criteria for nontarget lesions**

Response	Evaluation of Nontarget Lesions
Complete response (CR)	the disappearance of all nontarget lesions and normalization of tumor marker levels. All lymph nodes must be non-pathological in size (<10mm short axis)
Non-CR/non-PD	the persistence of one or more nontarget lesions and/or maintenance of tumor marker levels above the normal limits
Progressive disease (PD)	the appearance of one or more new lesions and/or unequivocal progression of existing nontarget lesions

## **8.4 Criteria for Progressive Disease.**

### **8.4.1. Measurable soft-tissue lesions**

When evaluating soft-tissue lesions, the definitions in Table 5 apply:

In some circumstances, it may be difficult to distinguish residual disease from normal tissue. When the evaluation of complete response depends on this determination, it is recommended that the residual lesion be investigated (e.g. fine needle aspirate or biopsy) before confirming the complete response status.

Progression in a nodal or visceral site should be defined using RECIST1.1 (Table 5).

### **8.4.2 PSA**

Per the PCWG3, PSA progression is defined as the date that a 25% or greater increase and an absolute increase of 2 ng/mL or more from the nadir is documented and confirmed by a second value obtained 3 or more weeks later. Where no decline from baseline is documented, PSA progression is defined as a 25% increase from the baseline value along with an increase in absolute value of 2 ng/mL or more after 12 weeks of treatment.

### **8.4.3 Bone**

Progressing disease on bone scan is considered when at least 2 new lesions are observed. Yet, progression remains unconfirmed unless at least 2 *additional* new lesions appear at a subsequent time point.

Unless clinically indicated, there is no need to perform a follow-up bone scan before 12 weeks of treatment. To define disease progression requires a confirmatory scan (which shows additional new lesions compared with the first follow-up scan) performed 6 or more weeks later. When further progression is documented on the confirmatory scan, the date of progression recorded for the trial is the date of the first scan that shows the change.

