Expected enrollment	30 patients (Up to a max of 10 patients with non-BRCA1/BRCA2/ATM homologous recombination DNA-repair mutations allowed, ensuring at least 20 BRCA1/BRCA2/ATM-positive patients).
Rationale	
At the time of metastatic disease, continuous ADT (+/- docetaxel, +/- abiraterone) is commonly initiated for the treatment of prostate cancer. However, many men find it difficult to tolerate treatment-related toxicities, including sexual impotency, decreased libido, hot flashes, and weight gain. These symptoms can persist with the development of castration resistance. Treatment with non-AR targeted agents, such as PARPi, may avoid or delay the toxicities of hormonal therapy. Therefore, there is an unmet medical need to develop non-hormonal therapies for men with newly diagnosed metastatic prostate cancer who wish to avoid or defer the initiation of chronic ADT. There is also a similar need for those patients with biochemically recurrence prostate cancer at high risk of developing metastatic disease (i.e. PSADT <math>\leq</math> 9 months).
 
The clinical activity of PARPi in patients with homologous recombination DNA-repair mutations and metastatic prostate cancer has now been established. Focusing specifically on patients with an inactivating mutation in a pre-specified group of DNA-repair genes, we hypothesize that targeted therapy with PARPi should be sufficient to induce a clinical response irrespective of hormonal (castration-sensitive or castration-resistant) status. Our hypothesis is based largely on the data from Mateo et al (NEJM 2015) showing a clinical response rate to olaparib of 88% in a heavily pre-treated population of mCRPC patients with a DNA repair mutation, with the most pronounced responses being in men with germline inactivation.(1) For men with metastatic hormone sensitive prostate cancer (mHSPC) and high risk biochemically recurrent disease (BCR), this trial would also provide an alternative to ADT. However, given that primary ADT (in mHSPC and high risk BCR) is a standard first-line therapy, all patients on trial must be ineligible for or decline standard-of-care hormonal treatment. For patients with mHSPC who do not respond to PARPi, we have incorporated safety rules into the trial design to take patients off study at first signs of progression. Primary ADT (+/- docetaxel, +/- abiraterone) would still remain a treatment option upon progression.
 
The primary hypothesis of this study is that outcomes for patients with mHSPC and high risk BCR with an inactivating homologous repair mutation will be improved by this therapeutic agent (rucaparib)

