## 5. TREATMENT/INTERVENTION PLAN

The following assessments and procedures will occur during the study. A schedule of assessments is provided in Table 1.

	Pre-study	Study Period				Off Treatment / Follow-up
		On Treatment Assessments (Every 28 days) 				
	Day -7 a, h ( $\pm 7$ days)	C1D1 h ( $\pm 3$ d)	C2D1 h ( $\pm 3$ d)	C3D1 h ( $\pm 3$ d)	CnD1 h ( $\pm 3$ d)	
Informed consent	X					
Demographics	X					
Medical history	X					
EKG	X					
Focused Medical history		X	X	X	X	X
Physical exam	X	X	X	X	X	X
Vital signs (P, BP, RR, T)	X	X	X	X	X	X
Height	X					
Weight	X	X	X	X	X	X
Performance status	X		X	X	X	X
Toxicity assessment	X		X	X	X	X
Concomitant meds	X	X	X	X	X	X
Metastatic tumor biopsy	X e				(X) e	
ctDNA (10ml)		X g				X g
Radiologic tests b	X				X b	X b
Laboratory tests c	X	X f	X	X	X	X
Rucaparib		X	X	X	X	
Adverse events			X	X	X	X

Table 1 Study Calendar

Abbreviations: CBC, complete blood count; CT, computerized tomography; MRI, magnetic resonance imaging; PSA, prostate-specific antigen

a Informed consent and radiologic assessments should be obtained within 8 weeks of study start date. EKG should be obtained within 28 days of study start date.

b Radiographic evaluations (CT A/P and NM Bone Scan) every 3 months (if metastatic disease) or every 6 months (for BCR) while enrolled in the study). They are needed within 8 weeks of screening; if previously performed then they are to be performed at screening. CT A/P and NM Bone Scan are to be performed at off-treatment visit if they have not been performed in the prior month.

c CBC w/diff, Complete Metabolic Panel, PSA, lipid panel at each visit. Testosterone, PT/INR, PTT, and Urinalysis at screening visit only and should be obtained within 28 days of study start date.

d Subjects will be followed after completion of rucaparib therapy monthly until toxicities resolve to grade 0-1. No post treatment follow up visit needed otherwise.

e Only for patients with metastatic disease: MANDATORY soft tissue Core tumor biopsy performed pretreatment (Day -7 +/- 7 days), bone biopsies are optional at pretreatment. OPTIONAL soft tissue and bone tumor biopsy on C4D1 (+/- 7 days)

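### Bone progression is defined differently in Sections 8.2.5, 8.3.3 and 8.4.3, and the plan does not say how an unconfirmed bone progression enters the rPFS analysis

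*Combined protocol and SAP*

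**What the plan says.** **Bone rules.**
- Section 8.2.5: when the bone scan is the only sign, "disease progression in bone is defined as 2 or more new lesions seen on bone scan compared with a prior scan" taken for trial entry. Other imaging is called for if flare or trauma is suspected, and "If many new areas of uptake are observed, confirmation is generally not necessary".
- Section 8.3.3: absent clearly worsening soft-tissue disease or symptoms, "progression at the first scheduled assessment should be confirmed on a second scan performed 6 or more weeks later". It does not ask for further lesions on that second scan.
- Section 8.4.3: "Progressing disease on bone scan is considered when at least 2 new lesions are observed", but this stays unconfirmed unless at least two more appear later. The next paragraph says "To define disease progression requires a confirmatory scan (which shows additional new lesions compared with the first follow-up scan", at 6 or more weeks, and gives no number. A confirmed progression is dated back to the first scan.

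**rPFS definition and censoring.** Section 8.1.2.3 and the Synopsis endpoint use RECIST 1.1 for soft tissue, PCWG3 for bone, clinical events and death. Section 10.1.2.3 names RECIST 1.1 progression or death and no bone rule. Both the Synopsis and 10.1.2.3 censor men without progression at the last assessment that showed none, and both assign progression to the earliest observed time.

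**Removal and later imaging.** The Synopsis rationale and Section 1.3.1 speak of safety rules for mHSPC men who do not respond, "to take patients off study at first signs of progression". Section 6.4 lists symptomatic or radiographic disease progression without saying whether it must be confirmed. Section 5.5 repeats imaging at the end-of-treatment visit only if there was none in the prior 3 months; Table 1 footnote b says the prior month. Footnote d provides monthly follow-up until toxicities settle, and then "No post treatment follow up visit needed otherwise".

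**The concern.** Two things are missing: a single definition of a bone event, and a rule for a man whose first positive bone scan is never followed by a confirming one.

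The first is a consistency problem. Two sites enrol, and an assessor who follows 8.2.5 will record a different event, or a different date, from one who follows 8.4.3.

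The second can bias the estimate. Under 8.4.3 a man with two new lesions and no second scan has not met the definition. A literal reading of the censoring rule then puts him at his last clean scan. He would be censored because his bone disease appeared to progress, so the independent-censoring assumption of Kaplan-Meier fails and the median is pushed upward. If 8.2.5 is applied instead, every qualifying scan counts at once, and a flare that is not recognised could pull the median downward.

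**Working it through.** **1. The same scan under each section.** Take a metastatic man with two new lesions at his second scheduled scan, no suspected flare, no soft-tissue change and no further scan.

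| Section applied | Status for rPFS |
|---|---|
| 8.2.5 | Event at that scan |
| 8.3.3 | No confirmation requested, because this is not the first scheduled assessment |
| 8.4.3 | Unconfirmed |
| 10.1.2.3 (RECIST 1.1, with Table 6 and 8.2.7 on new lesions) | Event, if the new lesions are judged unequivocal |

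**2. Can the 6-week confirmation be obtained?** The inputs are 42 days (8.4.3); an end-of-treatment visit 28 ± 3 days after the last dose (5.5); and on-treatment scans every 3 cycles for metastatic disease or 6 cycles for BCR (5.2.1), that is 3 × 28 = 84 or 6 × 28 = 168 days.
- Last dose on the day of the first positive scan: the visit falls on day 25 to 31, before day 42. Under 5.5 no scan is due. No later imaging is scheduled.
- Last dose L days after that scan: the visit is on day L + 25 to L + 31. If footnote b triggers a scan, day 42 is reached at the end of the window when L + 31 ≥ 42, so L ≥ 11. At the nominal visit it needs L + 28 ≥ 42, so L ≥ 14.
- Treatment continued: the next scan comes 84 or 168 days later. Both exceed 42, and a confirmed event is dated back.

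The gap therefore concerns men who stop promptly, and most clearly those handled under 5.5.

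**3. Illustration of size.** The plan gives no expected median, event count or power for rPFS, so there is no stated figure to reproduce. Assumptions: exponential progression with a 12-month median; scans every g = 84/30.4375 = 2.76 months; a share b of first progressions seen on bone scan only; and all of these unconfirmed and censored at the previous scan.

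The probability of progressing in one interval is q = 1 − 2^(−2.76/12) = 0.147. Men censored at the previous scan are no longer at risk at the current one, so each scan multiplies the Kaplan-Meier estimate by (1 − q)/(1 − bq). The median is the first scan k at which [(1 − q)/(1 − bq)]^k falls to 0.5 or below.

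| b | Factor per scan | Estimate at scan k − 1 | Estimate at scan k | k | Median, months |
|---|---|---|---|---|---|
| 0% | 0.853 | 0.529 | 0.451 | 5 | 13.8 |
| 20% | 0.879 | 0.523 | 0.460 | 6 | 16.6 |
| 40% | 0.906 | 0.501 | 0.454 | 8 | 22.1 |
| 60% | 0.935 | 0.513 | 0.479 | 11 | 30.4 |

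The comparator is 13.8, not 12: the first 1.8 months come from the scan grid alone. As a rough guide the median is multiplied by 1/(1 − b), that is 1.25, 1.67 or 2.5, and rounded up to a scan date. The 40% row is close to the edge, since the estimate one scan earlier (19.3 months) is 0.501.

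**4. Sensitivity.**
- Half of the bone-only events confirmed (replace b by b/2): 13.8, 16.6 and 19.3 months, so there is no shift at a 20% share.
- Assumed median 9.8 months, the PFS figure that Section 1.3.1 quotes for olaparib in repair-deficient mCRPC: 11.0 becomes 13.8, 16.6 or 24.8. With half confirmed it is 11.0, 13.8 and 13.8.
- Assumed median 6 months with a 20% share: 8.3 in both cases, no shift.

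**The case against.** A reader might infer that the confirmation cannot be met at all because men leave at the first sign of progression. The documents do not support that. The first-signs wording is rationale text limited to non-responding mHSPC men, and Section 1.3.1 phrases it as an intention. The operative list in 6.4 says only disease progression. If 8.4.3 also governs removal, an unconfirmed scan is not yet progression, the man stays on treatment, and his next scheduled scan satisfies the 6-week rule. Footnote b can also yield a late enough scan.

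A reader might also infer that the plan inflates rPFS. That needs three conditions together: 8.4.3 applied strictly, departure before confirmation, and censoring at the earlier scan. No passage orders that censoring for a man with new lesions, and assignment to the earliest observed time points the other way. Soft-tissue progression, clinical events and death still count under 8.1.2.3.

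The reference in 8.4.3 to the first follow-up scan could be read together with 8.3.3. This narrows the conflict but does not remove it: 8.3.3 asks for no additional lesions, 8.4.3 does, and 8.2.5 still counts the first scan.

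The illustration is a worst case that also scans every man at 12 weeks, although BCR men are scanned at 24. With 28 men, all events observed and no bias, chance alone spreads the estimated median over roughly 8.3 to 19.3 months (central 95% of simulated trials, true median 12).

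What stands is that neither 6.4 nor any other passage says whether an unconfirmed scan triggers removal, none keeps a man on treatment until confirmation, and none says how such a man is analysed. Even a man kept on treatment may stop for PSA progression, which the Synopsis makes a stopping reason, before his next scan.

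**Conclusion.** The point holds as a conflict of definitions plus an unspecified analysis rule. The same bone scans can be an event, a pending event or a non-event, and a man who stops promptly after a first positive scan has no scheduled scan that meets 8.4.3.

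The bias is conditional: upward if 8.4.3 is applied and such men are censored at the last clean scan, possibly downward through flare if 8.2.5 is applied. Its size cannot be derived from the documents, because they give neither the share of bone-only progressions nor the share left unconfirmed. The shift from 13.8 to 16.6, 22.1 or 30.4 months is an upper illustration on assumed inputs. It shrinks to between nothing and 5.5 months (19.3 − 13.8) if half are confirmed.

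rPFS is secondary, reported as an estimated median with no test or threshold. The PSA50 decision and the two-stage design are unaffected. The change should be made, but the primary conclusion does not depend on it.

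**What to change.** State one bone-progression rule for the rPFS analysis and use it in Sections 8.2.5, 8.3.3, 8.4.3 and 10.1.2.3. Bring the event definition in 10.1.2.3 into line with 8.1.2.3 and the Synopsis.

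For a man who leaves before a confirmatory scan, count two or more new lesions as an rPFS event at the date of that scan. Add a sensitivity analysis that requires confirmation, and report how many bone events were unconfirmed.

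Reconcile the removal passages (Synopsis rationale, 1.3.1, 6.4) and the off-treatment imaging passages (5.5, Table 1 footnote b) with the confirmation rule. How removal is decided is a clinical matter, and no rule is proposed here.

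The analysis change costs wording and one extra analysis. Its downside is that some flare scans may be counted as events; the sensitivity analysis shows how much that matters.
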